## **Risks**

Most of the risks involved in the study relate to adverse events related to study medication. Chantix and bupropion are both approved by the Food and Drug Administration as an aid for smoking cessation. The most common adverse events associated with bupropion are headache, insomnia, rhinitis, dry mouth, and anxiety. Bupropion is associated with an increased risk (1/1000 at 300 mg/day) of seizures (GlaxoSmithKline, unpublished data). We will minimize this risk by screening out and preventing participants from using bupropion who are also currently using any additional form of bupropion, psychoactive medications, nicotine replacement therapy, fluoxetine, clonidine, buspirone, or doxepin in the past 30 days and those with: self-reported alcohol dependence within the past year; history of seizures or head trauma; history of bulimia or anorexia nervosa; pregnant (as measured by over the counter pregnancy test kit for women of child-bearing age only) or contemplating pregnancy; breast feeding; myocardial infarction in the past 30 days, and use of other forms of tobacco in the past 30 days. The most common adverse events associated with Chantix are nausea, changes in dreaming, constipation, gas, and/or vomiting. The FDA recently required new boxed warning for both these medications: people who experience any serious and unusual changes in mood or behavior or who feel like hurting themselves or someone else stop taking the medication. Chantix has no clinically meaningful drug interactions based on drug characteristics and clinical experience with the drug to date (Pfizer).

All participants requesting prescription medications, Chantix or Bupropion will be screened and medically cleared by the on-the-ground primary care physician. [name] will continue his role as reviewing study physician. [name] will provide secondary review of all screeners, and intake materials to make sure there are no contradictions to pharmacotherapy. We have a long track record of [name] reviewing all medication screeners and study documents on

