- Internet Session 1:** Participants will be asked to log into the website prior to the first session to allow for any problems with the site to be fixed prior to sessions starting. Participants who decide to take any study medication will need to visit the Polson Tribal Clinic in Polson, MT to pick up a one month supply of study medication. Any unused NRT or medication will be dropped off at the clinic and then mailed back to the research assistants by the clinic staff. The study physician will be available to answer additional

questions. Beginning with this session and continuing through all sessions. Topics we anticipate covering include, but are not limited to: preparing to quit, dealing with cravings, support systems, traditional tobacco, stress reduction, weight management, and staying quit, along with other topics determined during program development. For each session, the tribal college student will begin the session by answering a series of questions to produce an individually-tailored report that will be provided on the screen at the end of each week's session so that the smoker can work on strategies during the week before the next internet session. Estimated time for the web session is 30 minutes.

- **Internet Sessions 2-8:** *The second session is the quit date for all participants in the group.* Weekly procedures will follow the same format as for the first session. At the session dealing with traditional tobacco, participants will be asked to talk about their own use, though they will not be required to do so because this is not always culturally appropriate. Participants will be asked to fill out weekly brief surveys about their use of tobacco during the week; e-mail reminders will be sent. Participants will also be asked to fill out brief session evaluations on-line after each session; e-mail reminders will be sent for these as well. Session evaluations will go directly into a separate database that will be de-identified; participants will be told about this database to encourage more truthful responses.
- **Weeks 9-11:** Participants will receive one individual email per week from a research assistant.
- **Final Session- End of Treatment (Week 12):** Session content procedures will follow the same format as for other sessions. All participants, regardless of smoking status will receive a certificate of achievement for completing the program and will be asked to submit a saliva sample.

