Furthermore, KUMC will be specifically asking participants weekly about potential adverse events (via our web-based communication system). Any report of an urgent/emergent or unexpected medical encounter by a study participant would automatically trigger an inquiry by our study personnel to find out what happened, create an AE report and forward that to [name] and the on-the-ground physician to review and decide whether the AE was study or study medication related and whether participant should be taken off pharmacotherapy or should be advised to stop participating in the study.

Because the anticipated level of risk involved with all possible pharmacotherapy use is low, adverse events will be recorded and reported at the completion of the study along with other study results. In addition, serious adverse events will be monitored and handled as described below:

Definition: Consistent with the definition by the FDA, a serious adverse event includes any event experienced by a study subject while on the study medication that:

- Is fatal
- Is life-threatening (subject was at risk of death from the event as it occurred)
- Is disabling or incapacitating
- Requires inpatient hospitalization or prolongs a current hospitalization
- Is a congenital anomaly in the offspring of a subject who received the study medication
- Required intervention to prevent permanent impairment or damage

Monitoring: Information about serious adverse events experienced by study subjects will be monitored by the following means:

- Report given by study subjects to study staff either in person or by telephone
- Report given to study staff by study subjects' family or friends either in person or by telephone
- Report by the subject's physician or other health care provider involved in their care
- Report from a hospital or other healthcare facility where the study subject(s) is being treated for the serious adverse event
- Other persons that may have knowledge of such serious adverse event.

Procedure: Upon receiving report of a serious adverse event:

- The study staff will page [name] (at beeper [name]) as soon as possible
- The study staff will give the necessary information to [name]
- [name] will obtain other necessary information and complete the "MED WATCH" form for each serious adverse event
- [name] will make a decision whether to stop the study medication temporarily or permanently and inform study staff of this decision

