## **Suicide/Homicide Procedures**

Serious neuropsychiatric symptoms have occurred in patients taking Chantix. These symptoms include changes in behavior, agitation, depressed mood, suicidal ideation, and attempted and completed suicide. While some patients may have experienced these types of symptoms and events as a result of nicotine withdrawal, some patients taking Chantix who experienced serious neuropsychiatric symptoms and events had not yet discontinued smoking. In most cases, neuropsychiatric symptoms developed during Chantix treatment, but in others, symptoms developed following withdrawal of Chantix therapy.

As a result, special caution must be taken if a participant reports an *increase in depressed mood, agitation, changes in behavior not typical for them, or **suicidal thoughts or action** since starting the study medication*. The suicide/homicide protocol will be instituted for all participants noting changes of this sort since starting Chantix.

The suicide/homicide protocol is as follows:

1. Ask participant to describe their symptoms in more detail.

*“Tell me more about what you are experiencing.”*

2. Assess the level of severity.

*“In general, would you say these symptoms are mild, moderate or severe?”*

3. Assess attribution of symptoms to the study medication.

*“Do you believe these symptoms are caused by the study medication or another cause?”*

4. Assess suicide/homicide risk

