### Course of Action

1. If a participant reports **any** suicidal/homicidal ideation, including passive ideation (e.g., thoughts of death, would be better off dead, doesn’t care about living, etc.) or active ideation (has intent to harm, a plan, and means) advise them to stop taking the medication immediately.
2. If the participant is exhibiting active suicidal or homicidal ideation and DOES intend to harm him or herself or someone else:
  - a. Each local mental health center office provides 24 hour a day telephonic crisis response for any citizen in crisis. After discussing the person's problems on the phone the mental health professional (MHP) will decide whether a face to face evaluation is needed.
  - b. Where full time dedicated MHP teams exist, emergency crisis services are available to all persons for both telephone crisis support and face to face evaluations, where clinically indicated, on a 24/7 basis. In offices without dedicated full time crisis teams, clinicians are on call to respond to emergency requests for evaluation and dispositions only for WMMHC clients.
  - c. When a person is judged not to be in an emergency situation, as defined in Montana statute, the person may be given an emergency appointment at the local center for the next day, or referred to a local hospital for voluntary psychiatric admission, or linked with other community resources as appropriate.
  - d. If the individual has a primary therapist, who is not affiliated with the mental health center, that primary therapist will be contacted as soon as practical by the MHP.

- e. Stay with the participant until the crisis worker is able to intervene.
3. If the participant is exhibiting passive suicidal or homicidal ideation and does NOT intend to harm him or herself, the counselor should provide the participant with the **Mental Health Resource Card** and the **Crisis Referral List**. The counselor should also encourage the participant to seek support from friends, family, and possibly mental health resources.
4. If there is no suicide risk but the participant reports neuropsychiatric symptoms (increase in depression, change in mood, agitation, etc.) that are more than mild and that they attribute to the study medication, advise them to stop taking the medication immediately.

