5. Regardless of the level of threat, a detailed case note must be made on the Adverse Event Report Log and Drs. [name] and [name] must be contacted immediately. *Please note: **If a participant is actively suicidal, the first priority is to ensure their safety. Drs. [name] and [name] should be contacted after the Crisis Worker has intervened.***

**Plans for Assuring that any Action Resulting in Temporary or Permanent Suspension of the Research is Reported to the NCI Program Director Responsible for the Grant.** Clinical research is subject to annual review and recertification by the Human Subjects Committee of the University of Kansas Medical Center. Any action resulting in temporary or permanent suspension of the research by the Human Subjects Committee, the FDA, or other authorized governmental agencies, will be reported to the NCI program director responsible for the grant.

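### The safety script advises stopping medication for more-than-mild non-suicidal neuropsychiatric symptoms only if the participant blames the drug, and sets no hold while a physician decides

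*Protocol*

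**What the plan says.** The stop rule is in the Protocol, Section VI, Suicide/Homicide Procedures, Course of Action. Item 4 deals with participants who have no suicide risk but report symptoms such as worsening depression, mood change or agitation "that are more than mild and that they attribute to the study medication, advise them to stop taking the medication immediately".

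The two conditions come from the interview script in the same section. Step 2 asks "In general, would you say these symptoms are mild, moderate or severe". Step 3 asks "Do you believe these symptoms are caused by the study medication or another cause".

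Other parts of the Protocol bear on the same situation:

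- **Section III, Risks**, describes the boxed warning on Chantix and bupropion as requiring that "people who experience any serious and unusual changes in mood or behavior or who feel like hurting themselves or someone else stop taking the medication".
- **Course of Action, item 1**, advises an immediate stop for any suicidal or homicidal ideation, whatever the participant thinks caused it.
- **Course of Action, item 5**, applies to every case: "Regardless of the level of threat, a detailed case note must be made on the Adverse Event Report Log", and two study physicians must be contacted immediately.
- **Section VI, reporting of adverse events**, has an urgent, emergent or unexpected medical encounter written up and sent to physicians to "review and decide whether the AE was study or study medication related and whether participant should be taken off pharmacotherapy".
- **Section V, Internet Sessions 2-8**: "The second session is the quit date for all participants in the group". Under Internet Session 1, participants taking medication collect a one-month supply.

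**The concern.** Item 4 makes an immediate safety instruction depend on a causal judgement by the person who has the symptoms. The Protocol itself shows why that judgement is unreliable. The opening of the Suicide/Homicide Procedures accepts that nicotine withdrawal may explain some of these symptoms, but adds that "some patients taking Chantix who experienced serious neuropsychiatric symptoms and events had not yet discontinued smoking". Withdrawal therefore cannot account for all cases.

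The trial schedule makes drug effect and withdrawal harder to separate. Everyone has a quit date at the second session, so attributing agitation or low mood to quitting is a ready answer. That answer removes the stop advice.

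What is at stake is the interval between staff contact and the physician's decision. The participant may have up to a month's medication at home, so what staff say at contact can decide whether the next dose is taken. For serious symptoms blamed on something else, the script is less protective than the warning the Protocol summarises.

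**Working it through.** The plan states no figure to reproduce. The check compares the rules and then counts the answers that the script allows.

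**1. The rules side by side**

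| Place in the Protocol | Trigger | Is perceived cause a condition? | Action at contact |
|---|---|---|---|
| Section III, Risks (boxed-warning summary) | Serious and unusual mood or behavior change, or feeling like hurting self or others | No | Stop |
| Course of Action, item 1 | Any suicidal or homicidal ideation | No | Stop advised |
| Course of Action, item 4 | Non-suicidal symptoms, more than mild | Yes | Stop advised only if blamed on the drug |
| Course of Action, item 5 | Every case | No | Case note and physician contact; no hold stated |
| Section VI, adverse events | Urgent, emergent or unexpected medical encounter | No; physicians judge relatedness | Physician decides; no hold stated |
| Section VI, serious adverse events | Event meeting the seriousness definition | No | Physician is paged and decides; no hold stated |
| Section III, Risks (discontinuation) | Pregnancy, other bupropion-containing drug, contraindication | No | Discontinue; neuropsychiatric symptoms not listed |

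Item 4 is the only rule here that uses the participant's opinion of cause as a gate.

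**2. Count of script outcomes for a non-suicidal participant**

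Inputs: 3 severity answers (step 2) and 2 cause answers (step 3).

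Combinations: 3 × 2 = 6.

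| | Study medication | Another cause |
|---|---|---|
| Mild | No stop advice | No stop advice |
| Moderate | Stop advised | No stop advice |
| Severe | Stop advised | No stop advice |

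- Stop advice under item 4: 2 of 6.
- More than mild but no stop advice: 2 of 6.
- Stop advice if the attribution clause is deleted: 2 + 2 = 4 of 6.

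If a participant who is unsure is counted as a third cause answer, there are 3 × 3 = 9 combinations. Unsure is not attribution to the drug, so stop advice stays at 2 and the more-than-mild combinations without it rise to 2 × 2 = 4. Deleting the clause gives 2 × 3 = 6 of 9.

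These counts describe the rule. They are not weighted by how often each answer occurs, so they do not measure risk.

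**3. Where the conflict with Section III lies**

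Severity is not the problem. More than mild is a lower threshold than serious and unusual, so for moderate symptoms blamed on the drug item 4 may go further than the warning. The conflict is in the attribution clause, and it is clearest for severe symptoms blamed on another cause. Section III would have that participant stop; item 4 gives no such advice.

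**The case against.** The strongest reply is that the gap is small. Item 5 sends every case to two physicians at once, and there is further cover: a 24-hour telephone line, weekly questions about adverse events with follow-up calls, and a local physician. Harm requires a dose taken before the physicians decide, and the documents give neither a response time nor a dosing schedule. This stands as a limit on size. It does not remove the point, because none of these provisions tells the participant what to do with the drug in the meantime.

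A second reply is that the clause is sensible triage. Mood symptoms are foreseeable in new quitters, so non-physician staff stop what looks drug-related and refer the rest. That explains the referral. It does not explain leaving a severely affected participant on the drug on the strength of their own view of the cause.

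Third, Section III is a risk summary, not an operating rule. That is true, but staff will follow the script, and the script should not fall short of a warning the Protocol cites.

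Fourth, stopping for every more-than-mild symptom goes beyond the warning's wording for moderate symptoms, and the number of extra interruptions is unknown. Interruptions would also touch pharmacotherapy utilization, a secondary endpoint. This is fair, and it is why a temporary hold is an acceptable minimum. Deletion still keeps the Protocol's own severity threshold, and physicians can reverse the stop.

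Two further limits stand. The script is introduced for changes since starting Chantix, so editing item 4 alone does not clearly cover bupropion users. The drug-use instructions and consent text are not available here and may separately tell participants to stop.

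**Conclusion.** The concern holds and should be fixed. Item 4 ties stop advice to the participant's own attribution, the boxed-warning summary in Section III does not, and no hold is stated while a physician decides. Of the 6 severity-by-cause answers, 2 that are more than mild lead to no stop advice. One of these, severe with another cause, is the clear conflict with Section III; moderate symptoms need not fall under its wording.

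No event rate or expected number of affected participants is claimed, because the documents give none. The conclusion assumes that staff follow the script as written and that the interval before a physician decides can be long enough for a dose to be taken. The point concerns participant safety and does not alter the sample size or the primary analysis.

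**What to change.** Delete the attribution condition from item 4, so that any more-than-mild neuropsychiatric symptom leads to stop advice, and let the physicians contacted under item 5 decide on restarting. At minimum, instruct participants with any more-than-mild symptom to hold the drug until those physicians decide. Keep the step 3 answer as information for the physicians' causality review, not as a gate on the advice.

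The cost is a one-clause protocol amendment and brief retraining on the script, with no added visits or staff. The downside is some additional interruptions of medication, possibly temporary, including some for symptoms that are really nicotine withdrawal. The documents do not allow their number to be estimated.

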## **VII. Study Withdrawal/Discontinuation Procedures**

Participants may withdraw from the study at any time with no penalty for any reason. We will utilize whatever information we have at the time of withdrawal. All confidential information related to the participant who decides to withdrawal will be kept locked.

## **VIII. Plan for Assuring Subjects' Privacy and Confidentiality**

[name] will retain copies of the signed consent forms throughout the course of the study. Standard language in our consent form assures the participant of the confidential nature of our study. These standards are strictly adhered to and monitored by the University of Kansas Human Subject Committee. Assigning each participant a study number, numerically coding all data, and de-identifying all transcripts of focus group discussions will maintain confidentiality. A key linking ID numbers with and participants' names will be kept by [name] in a locked file cabinet. Only summaries of findings will be reported in any publications or presentations, with no identification of individuals, individual facilities, or individual tribes.

## **IX. Follow-Up**

Participants will be asked to return for a follow up session at 6 months after their first initial group or individual meeting.

## **X. Record Retention**

All physical records will be kept in locked filing cabinets in offices that are kept locked when unoccupied. Subject files will be kept in a secure area, with access only by designated staff members (PI and Co-Investigators). The KUMC Department of Preventive Medicine has a well-developed structure for data management. Working data is maintained on a single large file server. Inactive files are moved to archival storage under control of an automated system, itself controlled by a DBMS (Ingres) based request system that ensures that all data movement is appropriately logged and commented. The archival storage is hosted on the institutional mainframe computer, which also supports billing and registration. The use of the mainframe ensures several high level support functions for the archive system (e.g., storage in separate fire zones, regular copying of data to new media, and guaranteed availability).

Data security and access will be governed by standard procedures. All analyses are logged with respect to IRB authorization, accounting information, principal and secondary investigators, statistician, and data analyst involved in the analysis. In order to create a unified data management strategy, we will identify all subjects with a sequentially assigned subject number and subject initials. To ensure subject confidentiality, no names, social security numbers, hospital or clinic numbers will be included in the shared databases. Names, addresses, telephone numbers, and any other information needed for recruitment, study involvement, and tracking will be obtained and maintained locally by the project personnel. All computer files and systems will be password protected and accessible only by authorized personnel.

In accordance with KUMC's Research Institute, Inc.'s Research Records Retention Policy (2004), Research Records are to be retained by the University of Kansas Medical Center (KUMC) for a period of six (6) years after the submission of the final report and close-out procedures on the research project for which the Research Records were prepared, unless a longer retention period is specified by the sponsor, funding source, or regulation. All research records and files related to this study will be destroyed 6 years after the completion of this study.
